#### **3.3.1 Analysis Populations**

The populations used for this analysis will include a Screened Population, Study Population, Study Population (Non-HSCT), CSF Population, Ambulatory Population, and the Caregiver Population. These populations are defined below.

##### **3.3.1.1 Screened Population**

The Screened Population consists of all subjects who sign informed consent (i.e., consented to participate in this clinical study).

##### **3.3.1.2 Study Population**

The Study Population consists of all subjects who met the inclusion/exclusion criteria for the study (i.e., as defined in Section 5 of the study protocol) and who signed informed consent (i.e., consented to participate in this clinical study).

##### **3.3.1.3 Study Population (Non-HSCT)**

The Study Population (Non-HSCT) consists of all subjects in the Study Population who have not had HSCT procedure. This population includes Prodromal and Symptomatic ALSP subjects.

##### **3.3.1.4 CSF Population**

The CSF Population consists of all subjects from the Study Population who consented to participate in the optional CSF Biomarker sub-study and have an evaluable baseline CSF biomarker measurement.

### 3.3.1.5 Ambulatory Population

The Ambulatory Population consists of all subjects in the Study Population who have the ability to ambulate with or without assistance, as collected in the CRF.

### 3.3.1.6 Caregiver Population

The Caregiver Population consists of all subjects in the Study Population who have a caregiver that has consented to the study.

## 3.3.2 Subgroups

[figure not shown]
Analyses will be performed on the following set of subgroups, as defined at baseline:

- **Prodromal:** ALSP subjects with CSF1R mutation, radiographic evidence of ALSP and who do not meet clinical criteria for Symptomatic ALSP.

Note: The criteria for Symptomatic ALSP is an answer of “Yes” to the questions Symptomatic ALSP on the demographics electronic Case Report Form (eCRF) page.

- **Symptomatic ALSP:** ALSP subjects with CSF1R mutation, radiographic evidence of ALSP and meeting clinical criteria.
- **Symptomatic ALSP (Non-HSCT):** Symptomatic ALSP subjects who have not had HSCT procedure.
- **Symptomatic ALSP (Prior HSCT):** Symptomatic ALSP subjects who have had HSCT procedure.

**Figure 2. Subgroup Allocation**

Note: Groups denoted with an asterisk (\*) are included in the Study Population (Non-HSCT).

## **4 Statistical Methods**

### **4.1 General Considerations**

#### **4.1.1 Timing of Analyses**

The data from this NHS will be reviewed on an ongoing basis. Interim summaries of the data may be performed to support ALSP clinical development. The purpose of an interim analysis (IA) is to provide an initial check of modeling and analysis assumptions and characterization of disease progression. An IA of data from 42 subjects in this study was conducted using a data cutoff of 22 September 2023, SAP dated 19 October 2023, and an interim database freeze date of 01 November 2023.

This SAP covers a second IA, with the database freeze date timed to coincide with the Phase 2 Study database freeze, helping to facilitate an integrated analysis of the two studies. The Phase 2 study protocol is titled, “A Phase 2 Safety, Tolerability, and Proof-of-Concept Study of VGL101 in Patients with Adult-Onset Leukoencephalopathy With Axonal Spheroids and Pigmented Glia (ALSP)” (VGL101-01.201), also known as the Ignite study, with its protocol V9.0 and corresponding SAP V2.0.

#### **4.1.2 Interim Analysis**

An IA of the integrated Illuminate Study was conducted in September 2023 with NHS data occurring on or before 22 September 2023. A second IA of the study will be conducted with NHS database freeze occurring on or around 11 April 2025.

#### **4.1.3 Software and Verification**

The statistical analyses will be conducted with the SAS® System software version 9.4 or higher with specific version details to be described in the Analysis Data Reviewer Guide (ADRG). Analysis datasets will be created following Clinical Data Interchange Standards Consortium (CDISC) standards. All analyses will undergo formal verification procedures to ensure accuracy and consistency. Specifically, results will be independently verified through separate programming prior to the release of draft statistical reports. Additionally, all documentation and reports will be reviewed by the lead statistician to confirm the accuracy and alignment of the analyses with the study objectives and planned methodologies.

#### **4.1.4 Sample Size and Power**

The sample size of approximately 60 subjects was determined without a formal power calculation and is expected to provide sufficient information to address the study objectives in this rare disease.

#### **4.1.5 Level of Significance**

Unless otherwise noted, all statistical tests will be two-sided with a significance level of 0.05. P-values greater than or equal to 0.001, in general, will be presented to three decimal places. P-values less than 0.001 will be presented as “<0.001”; p-values greater than 0.999 will be

presented as “>0.999”. Confidence intervals will be presented to one more decimal place than the point estimate.

#### **4.1.6 Multiplicity Control**

Given the exploratory nature of this study, there are no planned adjustments to individual p-value or intervals for multiple comparisons or multiplicity.

#### **4.1.7 Descriptive Statistics**

Descriptive statistics will be used to summarize data from this study.

In general, continuous data will be summarized with number of subjects (N), number of observations (n), arithmetic mean, standard deviation (SD), median, minimum, and maximum. For fluid biomarker variables, percent coefficient of variation (%CV), geometric mean, and percent geometric coefficient of variation (%gCV) will also be presented.

The minimum and maximum will be reported to the same number of decimal places as the raw data recorded in the database. The mean, median, lower quartile and upper quartile will be reported to one more decimal place, and the SD (and the standard error [SE], if applicable) will be reported to two more decimal places than the raw data recorded in the database. In general, the maximum number of decimal places reported shall be four for any summary statistic.

Categorical data will be summarized in terms of the number of subjects providing data at the relevant time point (n) and percentages. Percentages will be presented to one decimal place. Percentages will not be presented for zero counts. Percentages will be calculated using n (the number of observations with non-missing values) as the denominator. A missing category shall be included only for categorical variables where no data is available. The missing category will be omitted if there were no missing values for that variable.

#### **4.1.8 Definition of Baseline**

Unless otherwise specified, for all endpoints, baseline visit is defined as Study Day 1. If the Baseline visit is performed over more than 1 day, then the last day of the baseline assessments will be designated as Study Day 1.

#### **4.1.9 Definition of Study Day**

Study day is defined as:

- Pre-Baseline study day = Date of Assessment – Date of Baseline
- Post-Baseline study day = Date of Assessment – Date of Baseline +1

As per these algorithms, there is no Study Day 0.

#### 4.1.10 Study Visit

Scheduled subject visits (i.e., Screening/Baseline, Month 6, Month 12, Month 18, Month 24, Month 30, Month 36) will be determined by the visit as specified in the eCRF. That is, scheduled visits will not be windowed and the nominal visit value will be used for analysis.

To utilize as much data as possible for analysis, unscheduled and ET visits will be mapped to a scheduled visit for analysis using windows as defined below, which are to be used for analysis purposes only. Once analysis visit windows are assigned, all visits, including unscheduled and ET visits, are eligible to be flagged as the “analyzed record” within the analysis window. As such, a subject may have more than one record for each analysis visit window. The following rule for determining which record is flagged as the “analyzed record” is as follows:

- When available, data from the scheduled visit is always used.
- If data from the scheduled visit is not available, then data from the unscheduled or ET visit closest to the scheduled visit study day for that analysis window will be used, if available.

**Table 2. Study Visit Windows**

Analysis visit	Nominal visit	Analysis visit window (days)		
		Start	End	Target
Baseline	Baseline	-28	1	1
Month 6	Month 6	93	273	183
Month 12	Month 12	275	455	365
Month 18	Month 18	458	638	548
Month 24	Month 24	640	820	730
Month 30	Month 30	823	1003	913
Month 36	Month 36	1006	1186	1096

Unless unscheduled or early termination visits are assigned to a visit window and flagged for analysis, they will be excluded from the summary tables by visit but will be included in the listings.

#### 4.1.11 Handling of Missing data

Every effort will be made to obtain required data at each scheduled evaluation from all subjects. In situations where it is not possible to obtain all data, imputations of missing data may be necessary. Common situations are described below, and details for how missing data will be handled for specific clinical scales is detailed in the [Appendix](#).

#### **4.1.11.1 Missing Severity or Relationship for Adverse Events**

AEs with missing severity will have the severity imputed as ‘Severe’. AEs with missing relationship to study drug will have the relationship imputed as ‘Related’. Actual values will be presented in the data listing.

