Subjects who, in the discretion of the investigator, may be eligible for a VGL101 clinical study may be discontinued from this study at any time. For subjects who discontinue from this study to enroll in a VGL101 clinical study, all procedures, except the MRI, blood biomarker sampling, and CSF collection (for subjects in the CSF Sub-study), will be collected once for the Early Termination (ET) Visit of this study and for the Screening or Baseline Visit of the VGL101 clinical study and will be analyzed as part of both studies. If CSF biomarker collection is not included at the Screening or Baseline Visit of the VGL101 clinical study, CSF biomarker collection will be performed at the ET Visit of this study.

Number of Subjects

Approximately 60 subjects are planned for enrollment.

The study will enroll subjects with prodromal or definitive ALSP. Prodromal ALSP is defined as ALSP that satisfies the radiologic, but not the full clinical, criteria (see [Section 5.1](#), Inclusion Criteria). At sponsor discretion, enrollment of individuals with prodromal ALSP may be discontinued.

Treatment Groups and Duration

No study intervention will be administered. Subjects will be followed for up to 24 months (subjects who complete the study before implementation of Amendment 3) or 36 months (subjects who complete the study after implementation of Amendment 3).

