6 INVESTIGATIONAL MEDICINAL PRODUCT(S) AND CONCOMITANT THERAPY

6.1 Investigational Medicinal Product

No intervention will be administered. Subjects will receive their usual treatments for ASLP, as prescribed by their physicians.

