10.2.3 Recording and Follow-up of Adverse Events and/or Serious Adverse Events

Adverse Event and Serious Adverse Event Recording

- When an AE/SAE occurs, it is the responsibility of the investigator to review all documentation (e.g., hospital progress notes, laboratory reports, diagnostics reports) related to the event.
- The investigator will then record all relevant AE/SAE information on the Serious Adverse Event Form in the eCRFs.
- It is not acceptable for the investigator to send photocopies of the subject's medical records to the sponsor or designee in lieu of completion of the AE/SAE eCRF form.
- There may be instances when copies of medical records for certain cases are requested by the sponsor or designee. In this case, all subject identifiers, with the exception of the subject number, will be redacted on the copies of the medical records before submission to the sponsor or designee.
- The investigator will attempt to establish a diagnosis of the event based on signs, symptoms, and/or other clinical information. Whenever possible, the diagnosis (not the individual signs/symptoms) will be documented as the AE/SAE.

Assessment of Severity

- The investigator will make an assessment of severity for each AE and SAE that is reported during the study and will assign it to 1 of the following categories:
 - Mild: An event that is easily tolerated by the subject, causing minimal discomfort and not interfering with everyday activities.
 - Moderate: An event that causes sufficient discomfort to interfere with normal everyday activities.
 - Severe: An event that prevents normal everyday activities. An AE that is assessed as severe should not be confused with an SAE. Severe is a category that is used for rating the intensity/severity of an event. Both AEs and SAEs can be assessed as severe.
- An event is defined as “serious” when it meets at least 1 of the predefined outcomes as described in the definition of an SAE, not when it is rated as severe.

Assessment of Causality

- The investigator will make every effort to assess the relationship of the AE, if any, to the study procedures. Causality will be assessed using the ICH-recommended categories as presented below:
 - Not Related: An AE will be considered “not related” to the study procedures if there is not a reasonable possibility (defined below) that the event has been caused by the study procedures required by the study.

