## 2 Study Overview

The Illuminate study is a non-interventional, prospective, multicenter, observational, natural history study (NHS) of patients with ALSP and asymptomatic carriers of colony-stimulating factor 1 receptor (CSF1R) gene mutations, the causative mutation for ALSP. Potential study patients will be screened for study eligibility. Individuals who satisfy the study inclusion and exclusion criteria and who provide written informed consent will be enrolled in the study and followed for up to 36 months. Approximately 60 subjects are planned for enrollment. Inclusion and exclusion criteria are detailed in the study protocol.

[figure not shown]
Clinic visits to assess disease status will be conducted at Screening/Baseline and at Months 6, 12, 18, 24, 30, and 36. Each clinic visit will include clinical assessments (cognitive, motor, functional, psychiatric, severity of illness, and caregiver burden assessments) and imaging studies. Blood for biomarker analysis will be collected at Screening/Baseline and at Months 6, 12, 18, 24, 30, and 36. Adverse events (AEs) and concomitant medications and procedures will be recorded throughout the 36-month study.

An optional sub-study to evaluate levels of biomarkers in cerebrospinal fluid (CSF) is also included in this study and will be conducted at select study sites. A CSF sample will be obtained at Screening/Baseline and at Months 6 (Brazil only), 12, 24, 36, and early termination (ET) visits for from subjects who provide informed consent to participate in the optional CSF Biomarker Sub-study. ET visit is mapped in the Electronic Data Capture (EDC) system as the nearest relevant visit in based on days from screening, typically the next subsequent visit.

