#### **4.5.3 Adverse Events**

AEs will be mapped to a MedDRA version 24.0 or higher. Severity will be assessed by the investigator.

The following AE summaries will be performed:

- AEs summarized by PT and SOC
- AEs summarized by PT and SOC by severity
- AEs related to study procedures summarized by PT and SOC.
- Serious AEs (SAEs) summarized by PT and SOC

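### The SAP's rule for a missing AE relationship names study drug, which this study does not give, and leaves a missing relationship to study procedures without a rule

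*SAP*

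**What the plan says.** SAP 4.1.11.1, headed "Missing Severity or Relationship for Adverse Events", has two imputation rules. Missing severity is set to the worst category, Severe. For causality, "AEs with missing relationship to study drug will have the relationship imputed as ‘Related". It adds: "Actual values will be presented in the data listing". Imputation can therefore affect summaries but not listings.

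The study has no drug. Protocol 6.1 says "No intervention will be administered", the protocol synopsis says "No study intervention will be administered", and SAP section 2 says "The Illuminate study is a non-interventional, prospective, multicenter, observational, natural history study (NHS) of patients with ALSP".

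The causality actually assessed is set out in protocol 10.2.3: "The investigator will make every effort to assess the relationship of the AE, if any, to the study procedures". Both permitted answers, Related and Not Related, are defined there against study procedures. SAP 4.5.3 carries this into one planned attribution summary: "AEs related to study procedures summarized by PT and SOC".

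**The concern.** The rule and the data it is meant to serve do not meet. The rule names an attribution that no section of either document arranges to collect. The attribution that is collected and reported has no missing-data rule.

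The pairing of missing severity with Severe and missing relationship with Related shows a conservative purpose: an unassessed event should count against the study, not disappear from a table. As written, the causality half does not achieve this. If the procedure relationship is blank, nothing puts the AE in the procedure-related table.

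That table matters in this study. Protocol 2.3 describes the risks of taking part as mainly those of blood sampling and, in the optional sub-study, lumbar puncture. Procedure attribution is thus the main safety question the study can answer about itself. The protocol wording cannot quietly correct the SAP, because SAP section 1 makes the SAP the governing document for the analyses. SAP 4.1.3 also calls for independent verification by separate programming, and two programmers could reasonably implement this sentence differently.

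**Working it through.** There is no stated figure to reproduce, and the documents give no AE counts. The check sets the texts side by side and follows the rule through to the planned tables.

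**Step 1: what each place refers to**

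| Place | Attribution named |
|---|---|
| SAP 4.1.11.1, imputation rule | Study drug |
| Protocol 6.1, protocol synopsis, SAP section 2 | No drug in this study |
| Protocol 10.2.3, causality assessment and definitions | Study procedures |
| SAP 4.5.3, attribution table | Study procedures |

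**Step 2: is there a rule elsewhere?** The rest of the SAP missing-data text (4.1.11, 4.1.11.2 and 4.1.11.3) deals with missing data in general, incomplete dates and alphanumeric laboratory values. Protocol 9.3 describes the AE summaries without a missing-data rule. None of these covers a missing procedure relationship.

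**Step 3: consequence for the 4.5.3 table.** Let N be all AEs, k the AEs recorded as related to study procedures, and m the AEs with that relationship blank.

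| How 4.1.11.1 is implemented | AEs in the procedure-related table |
|---|---|
| Drug relationship treated as not applicable, rule never triggered | k |
| Drug relationship treated as missing for all AEs, drug flag kept separate | k (with a drug flag of Related on all N AEs, used in no table) |
| Rule read as meant for study procedures | k + m |
| Imputed drug flag wrongly fed into the procedure table | N |

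Under either of the first two implementations, the table falls short of the conservative result by (k + m) − k = m. The last row would be a programming error and not a plan; it appears only because the wording does not exclude it.

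**Step 4: how large is m?** It is not given. Protocol 10.2.3 requires the investigator to document a causality assessment for each AE and SAE in the medical note, and to make one before the first transmission of an SAE. Blanks should therefore be few, and rarer still for SAEs. They are not excluded, since an assessment in the note can still be missing from the eCRF.

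**The case against.** The strongest reply is that this is carried-over wording whose meaning is easy to recover. The section heading refers to relationship in general, the only relationship assessed is to procedures, and the only attribution table is for procedures. A sensible programmer would apply the rule to the procedure field, which is the repair proposed here. Blanks should also be rare, given the causality requirement in protocol 10.2.3. Both arguments bear on consequence and both stand. Neither makes the sentence correct, and a governing analysis document should not depend on the programmer guessing what was meant.

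A reader might go further and infer that, because relationship to drug is absent for every AE, the rule turns every AE into a Related one. The documents do not support stating that as the result. A field that is never collected can equally be read as not applicable, in which case the rule never operates. The eCRF is not among the documents, so this cannot be settled. Even on the literal reading, no drug-related table is among the four AE summaries in SAP 4.5.3, and listings show the recorded values.

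A reader might also infer that the flag would spoil a comparison of harms with the Phase 2 VGL101 study. SAP 4.1.1 and 4.3.3 do plan an integrated analysis, but neither says that AEs or their relatedness will be pooled or compared. The natural history subjects also cannot be described flatly as untreated: the note to exclusion criterion 12 in protocol 5.2 allows people to enrol after finishing a VGL101 study.

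**Conclusion.** The rule is wrong as written, at low severity. SAP 4.1.11.1 imputes an attribution that this study does not provide for, and leaves the attribution it does assess and tabulate without a rule. The effect on a reported result is limited to the procedure-related AE table, which may omit up to m events with a blank procedure relationship. The number m is unknown, probably small and possibly zero.

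This rests on two assumptions: that the eCRF follows protocol 10.2.3 in recording relationship to procedures, and that no rule for that field exists in a specification outside the two documents. The evidence does not support a claim that all AEs would be reported as Related, or that a cross-study safety comparison would be compromised.

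**What to change.** In SAP 4.1.11.1:

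- Replace study drug with study procedures, so that a missing relationship to study procedures is imputed as Related.
- State that the imputed value is the one used in the SAP 4.5.3 table of AEs related to study procedures.
- State that relationship to study drug is not applicable in this study and will be neither derived nor imputed.

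The cost is a small edit to one section of the SAP and the matching line in the analysis dataset specification. The downside is at most m more AEs shown as procedure-related, which is the conservative result the rule was evidently written to give. Reporting the number of imputed values in a footnote to the table would let readers see how much of the count is imputed.

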#### **4.1.11.2 Imputation of Incomplete Dates**

An incomplete date is any date for which either the day, month or year is unknown, but all three fields are not unknown. An incomplete date occurs when the exact date an event occurred or ended cannot be obtained from a subject. However, a complete date is often necessary to determine if the event should be included in the analysis or to establish the duration of an event. In such cases, incomplete dates will be imputed.

Incomplete or missing start and end dates will be imputed for the following:

- Adverse events
- Medications to determine when the medication was taken (i.e., prior to Baseline or concomitant).
- Procedures to determine when the procedure occurred (i.e., prior to Baseline or concomitant).
- Date of birth will be imputed to determine age at Baseline and age at time of ALSP diagnosis. (Note: if “Birth Date” is incomplete/missing but “Age at Diagnosis of ALSP” is not missing, then the imputed birth date will not be used for the calculation of “Age at Diagnosis of ALSP” and the value recorded in the EDC will be used).
- ALSP diagnosis date will be imputed to determine duration from time of ALSP diagnosis to Baseline.

For the purposes of handling partially reported start and end dates for AEs, medications, procedures, and therapies, the following algorithm will be applied:

